1.0 BACKGROUND AND RATIONALE

1.1 Study Synopsis

This multicenter phase II study in 20 patients with BRAF^{V600} mutant disease (specifically BRAF^{V600E} or BRAF^{V600K} designated as BRAF^{V600E/K}), unresectable stage III/IV melanoma is designed to explore the mechanisms by which tumors acquire resistance to the combination of a BRAF inhibitor (dabrafenib;Tafinlar®) and MEK inhibitor (trametinib;Mekinist®). Tissue will be collected at baseline and at progression. If a subject is removed from the study for one of a variety of reasons including, but not limited to, an inability to tolerate the combination of dabrafenib and trametinib, a need to receive other therapy or completion of 3-years of study treatment without progression, and the subject later receives, as part of his/her standard of care, the combination of dabrafenib and trametinib and progresses on the standard of care regimen, then the subject may be contacted by the treating physician to be put back on to the LCCC 1128 protocol and have a progression biopsy at this progression time point. Markers of resistance will be explored by performing near kinome-wide profiling on tumor samples, and in patients who co-enroll in institutional protocol LCCC1108, by sequencing tumors using NextGen DNA sequencing technology. Overall response rate and duration to this combination will also be assessed.

1.2 Melanoma

Melanoma is the sixth most common malignancy in the United States and its incidence is increasing faster than any other cancer [1, 2]. Patients with metastatic melanoma have a median life expectancy of only 8 months. In the extension cohort from a recent phase I trial of the BRAF inhibitor vemurafenib, 81% (26 of 32) of patients with BRAF^{V600E/K} melanoma experienced at least 30% tumor shrinkage by RECIST with a complete response seen in two patients [3]. However, resistance to PLX4032 emerged after response durations of 2 to more than 18 months. Several key resistance mechanisms have been described and warrant further investigation. These mechanisms include new functional mutations in one of five established resistance genes (BRAF, NRAS, MEK1, MAP3K8 or COT, and PTEN).

MEK is a key protein integral to the RAS/RAF/MEK/ERK signaling pathway. In BRAF mutant melanoma, MEK activation drives disease proliferation. Therefore, it is hypothesized that the combination of BRAF and MEK inhibition is likely to have less downstream resistance than BRAF inhibition alone.

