2.2 Secondary Objectives

2.2.1 To explore whether resistance to BRAF and MEK inhibition is associated with new functional mutations in the approximately 150 oncogenes / tumor suppressor genes that are assessed in more than 10% of the tumors (using NextGen DNA sequencing technology) in the subset of patients who co-enroll in LCCC1108, with particular focus on one of five established resistance genes (BRAF, NRAS, MEK1, MAP3K8 or COT, and PTEN)

2.2.2 To determine the overall response rate (ORR: complete response + partial response) as measured via RECISTv1.1

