3.0 PATIENT ELIGIBILITY

3.1 Main Study Inclusion Criteria

Subject must meet all of the inclusion criteria to participate in this study:

- 3.1.1 Age ≥ 18 years
- 3.1.2 Signed written informed consent
- 3.1.3 Histologically confirmed V600E or V600K BRAF mutant melanoma
- 3.1.4 Unresectable Stage III/IV melanoma
- 3.1.5 ECOG PS 0-2
- 3.1.6 Normal organ function as defined by the following:
- Absolute neutrophil count $\geq 1.2 \times 10^9/L$
 - Hemoglobin ≥ 9 g/dL, platelets $\geq 75 \times 10^9/L$
 - PT/INR and PTT $\leq 1.5 \times$ ULN (Note: subjects receiving anticoagulation treatment may enroll with INR established within the therapeutic range prior to D1 of treatment)
 - Albumin ≥ 2.5 g/dL
 - Total bilirubin $\leq 1.5 \times$ ULN (patients with elevated bilirubin due to Gilbert's disease will not be excluded)
 - AST and ALT $\leq 2.5 \times$ ULN
 - CrCl ≥ 50 mL/min per Cockcroft-Gault
- 3.1.7 Prior anti-cancer treatment related toxicities except alopecia and lab values as outlined in section 3.1.6 must be \leq Grade 1 as per NCI CTCAEv4.
- 3.1.8 Willing to undergo biopsy for research purposes only (see section 6.6). **Note:** If possible, the pre-treatment biopsy should be performed after all other eligibility criteria are confirmed. Please also see the note in section 6.9.3 regarding assessment of biopsied lesions per RECIST v1.1.
- 3.1.9 Females of child-bearing potential: willing to use two forms of effective contraception, and to continue use for 16 weeks (4 months) post last dose of study medication. Effective contraception is defined as:
- An intrauterine device with a documented failure rate of less than 1% per year.
 - Male partner sterilization prior to the female subject's entry, and this male is the sole sexual partner for that female.
 - Complete abstinence from sexual intercourse for 14 days prior to enrollment, throughout study treatment, and for at least 4 months after the last dose of study treatment. Abstinence is only acceptable when in line with the preferred and usual lifestyle of the subject. Periodic abstinence (e.g. calendar, ovulation, symptothermal, post-ovulation methods, etc) and withdrawal are not acceptable methods of contraception.

- Double-barrier contraception: condom and occlusive cap (diaphragm or cervical/vault caps) with a vaginal spermicidal agent (foam/gel/cream/suppository).

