univariate analysis of kinase expression will be carried out to identify differentially expressed kinases after FDR adjustment. Since multiple kinases work in concert to regulate their functions, prediction analysis of microarrays (PAM) based on nearest shrunken centroid [9] will also be carried out to identify a subset of kinases that predicts resistance to BRAF+MEK inhibition. We also plan to utilize the kinome pathway as prior information in the analysis for identifying functionally related kinase sets to improve statistical power. Focusing on kinase sets may yield more reproducible and interpretable results.

Fisher's exact test will be carried out to test for association between the mutations at baseline to mutations upon the development of resistance to BRAF + MEK inhibition in each oncogene/tumor suppressor gene. Tumor samples from patients who progress while on study and those who are removed from study and who later progress on the combination treatment will be analyzed as one data set. The p-values will be adjusted via FDR to account for multiple comparisons.

The response rate will be estimated and 95% confidence interval will be computed. Progression-free survival will be evaluated using the Kaplan-Meier method. All demographic and analytic data will be summarized by descriptive statistics. Categorical data will be summarized using frequency tables whereas summary statistics such as means, medians, standard deviation and range will be provided for continuous data.

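### Eligibility makes BRAF mutated at baseline in every patient, and 8.1 does not set V600E/K aside, so gene-level testing cannot register a second BRAF alteration

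*Combined protocol and SAP*

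**What the plan says.** Three parts of the combined protocol and SAP bear on this point.

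- **Eligibility (3.1.3)** requires "Histologically confirmed V600E or V600K BRAF mutant melanoma". No patient can enter without a BRAF mutation.
- **Secondary objective 2.2.1** asks whether resistance is associated with "new functional mutations in the approximately 150 oncogenes / tumor suppressor genes", "with particular focus on one of five established resistance genes (BRAF, NRAS, MEK1, MAP3K8 or COT, and PTEN"). It applies to the patients who co-enroll in LCCC1108, whose number is not given. Section 1.2 names the same genes, but as background, where it counts among the known mechanisms "new functional mutations in one of five established resistance genes (BRAF, NRAS, MEK1, MAP3K8 or COT, and PTEN").
- **Data analysis plan (8.1)** uses Fisher's exact test to "test for association between the mutations at baseline to mutations upon the development of resistance", and does so "in each oncogene/tumor suppressor gene". It adds: "The p-values will be adjusted via FDR to account for multiple comparisons". The FDR level for these tests is not stated.

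Section 8.1 does not say whether a gene counts as mutated because of any variant, a particular variant, or a newly acquired one. It does not mention the qualifying V600E/K mutation, and it does not say which two-by-two table is tested. Section 1.6.2 reports that the sequencing platform has found functional BRAF variants not previously described, so a second BRAF alteration could be seen in the data.

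**The concern.** The objective is about gaining a mutation. A test on a yes/no status per gene can show a gain only in patients who start at no. For BRAF, eligibility puts every patient at yes. Of the five focus genes, BRAF is the only one that eligibility fixes as mutated.

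While V600 persists, a patient who acquires a second BRAF alteration has the same gene-level status as one who acquires nothing. The only change this coding can show is a lost V600 call, for example from low tumor content in the progression sample, and that runs in the wrong direction. A table giving p = 1 for BRAF beside informative p-values for other genes could be misread as evidence against acquired BRAF alterations, when the comparison carried no information.

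**Working it through.** The plan gives no power or p-value for the mutation tests, so there is no stated figure to reproduce. The power table in 8.1 concerns the kinase comparison and does not bear on this point.

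**Inputs**
- Baseline BRAF status: mutated in N of N (3.1.3).
- Sequenced pairs N: not given. I take 20, the planned enrollment, and then 15, 10 and 5.
- V600 persists at progression (assumption).
- BRAF alterations other than V600E/K at baseline: 0 of N (assumption).
- Genes tested: about 150 (2.2.1). FDR level: 0.05 (assumption, borrowed from the kinase analysis).
- k = number of patients who gain a second BRAF alteration.

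**Step 1. Gene coded mutated/not mutated, V600E/K counted**
- Time-by-status table [[N, 0], [N, 0]]: one column is empty, so p = 1. This holds for N = 5, 10, 15 and 20.
- Baseline-by-progression table [[N, 0], [0, 0]]: the not-mutated baseline row is empty, so p = 1. It stays at 1 even if V600 calls are lost: [[k, 20−k], [0, 0]] gives p = 1 for k = 0, 5, 10 and 20.
- Exact paired test: no gain is possible, so there are no discordant pairs and p = 1.

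The result does not depend on k.

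**Step 2. V600E/K left out of the coding**
- Exact paired test, k gains and no losses: p = 2 × 0.5^k.
- Time-by-status Fisher, [[0, 20], [k, 20−k]]: two-sided p = 2 × C(20,k)/C(40,k). For k = 6 this is 2 × 38,760/3,838,380 = 0.020.
- Baseline-by-progression table: [[0, 0], [k, 20−k]]. The mutated baseline row is now empty, and p = 1 for every k.

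| k of 20 | Step 1 coding | Exact paired | Time-by-status Fisher |
|---|---|---|---|
| 5 | 1.00 | 0.0625 | 0.047 |
| 6 | 1.00 | 0.031 | 0.020 |
| 8 | 1.00 | 0.0078 | 0.0033 |
| 10 | 1.00 | 0.0020 | 0.0004 |
| 11 | 1.00 | 0.0010 | 0.00015 |

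These p-values are unadjusted. The last line of Step 2 shows that recoding alone is not enough: the table must be chosen as well.

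**Step 3. After FDR adjustment**

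If BRAF were the only signal among 150 genes, its p-value would have to be at most 0.05/150 = 0.00033.
- Fisher, N = 20: 11 gains (0.00015); 10 gains (0.0004) fall short.
- Paired: 2 × 0.5^12 = 0.00049 falls short and 2 × 0.5^13 = 0.00024 passes, so 13 gains are needed and hence at least 13 sequenced pairs.
- Fisher with fewer pairs: 10 of 15 (0.00020) or 9 of 10 (0.00012). With 5 pairs even 5 of 5 gives only 0.0079, so no result can pass.

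**The case against.** The strongest reply is that 8.1 nowhere prescribes one yes/no status per gene. It compares mutations, and the governing objective asks about new ones. The V600 mutation that qualified the patient is by definition not new, so an analyst working from 2.2.1 might well set it aside. A reader might therefore infer from this point that the trial can never show a new BRAF mutation, or that BRAF findings are discarded. The documents do not support either inference. The coding is undefined rather than fixed, no text drops variant-level data, and 8.1 provides for frequency tables of categorical data, in which acquired BRAF variants can be reported.

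A reader might also infer that the problem has nothing to do with the choice of table. It does: once V600E/K is excluded, a baseline-by-progression association table, arguably the literal reading of 8.1, is still degenerate if no other BRAF alteration exists at baseline.

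Finally, what is lost is modest. BRAF is one of about 150 genes in an objective worded as exploratory. It is sequenced only in co-enrolled patients, and 6.7 gives kinome profiling priority when tissue is short. After FDR adjustment only a large number of acquired BRAF alterations would reach significance.

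All of this limits the claim but does not remove it. Testing by gene with no variant rule is most naturally read as gene-level status, and that reading makes the test uninformative for a named focus gene. If the coding stays open, it may be settled after the sequencing results are seen.

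**Conclusion.** The point holds in a limited form. Under gene-level mutated/not-mutated coding, the natural reading of 8.1, the BRAF comparison returns p = 1 whatever is acquired, as long as V600 persists. It then cannot inform one of the five focus genes of 2.2.1. Other codings are open to the analyst, and descriptive reporting survives under any of them.

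The gain from correcting this is the step from an uninformative test to one that can respond: unadjusted significance at 0.05 from 6 gains in 20 pairs (paired) or 5 in 20 (Fisher). The FDR-adjusted thresholds are much higher, and they become harder or impossible to reach as the number of sequenced pairs falls. These figures rest on persistent V600, no other BRAF alteration at baseline, and an FDR level of 0.05 with BRAF the only signal. The change should be made, but nothing in the primary objective or its sample size depends on it.

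**What to change.** Add three statements to the data analysis plan in 8.1, before the sequencing data are examined:

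1. Gene status is coded on functional variants other than the eligibility-defining BRAF V600E/K. For BRAF, mutated means a functional alteration in addition to V600E/K.
2. Presence of V600E/K is reported separately at each time point, as a check of tumor content.
3. For each gene, status at baseline and at progression is compared within patient by an exact paired test of gains against losses, in place of an association table of baseline against progression status. The FDR level and the number of genes in the adjustment are stated.

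Acquired BRAF variants should also be listed patient by patient, since with few sequenced pairs the list may say more than the test. The cost is a few sentences of text. No further samples, sequencing or patients are needed.

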1.3 Trametinib

Trametinib is a reversible and highly selective allosteric inhibitor of MEK1/MEK2. These characteristics, along with its long half-life, small peak/trough ratio and limited inter-subject variability in its pharmacokinetic (PK) profile, render it an excellent MEK1/MEK2 inhibitor to evaluate in human trials.[4] Trametinib is approved as monotherapy and in combination with

dabrafenib for the treatment of patients with unresectable or metastatic melanoma with BRAF V600E or V600K mutations.

1.3.1 Effects in Humans

The effect of trametinib in subjects with a variety of cancers has been evaluated in a number of studies, and additional studies are ongoing.[4] Trametinib has been administered as monotherapy in at least 9 of these studies, and as combination therapy in at least 10 additional studies. Please also review the package inserts for trametinib and dabrafenib for updated background information on each product.

Preliminary trametinib pharmacokinetics (PK) was determined after single- and repeat dose oral administration of trametinib tablets in subjects with solid tumors. Trametinib is absorbed rapidly with median T_{max} generally occurring within 1-3 hours after oral administration of trametinib under fasting conditions. Following repeat-dosing the mean area under the curve (AUC_{0-τ}) and maximum concentrations (C_{max}) increased in an approximately dose proportional manner. Trametinib accumulates with repeat dosing with a mean effective half-life at a dose of 2 mg of approximately 4 days.

In vitro, the metabolism of trametinib is mediated predominantly by non-CYP-mediated processes, via deacetylation alone, or with monooxygenation or in combination with glucuronidation biotransformation pathways. No formal clinical trials have been conducted to evaluate human cytochrome P450 (CYP) enzyme-mediated drug interactions with trametinib. Co-administration of trametinib (2mg per day) with the CYP3A 4 inducer dabrafenib (150mg BID) resulted in no clinically relevant pharmacokinetic drug interactions (trametinib package insert; January 2014). This protocol prohibits or cautions against the use of medications with the potential for drug interactions with dabrafenib. See section 4.5 (Concomitant Medications) and section 11.2 (Appendices) for the categories of medications that are prohibited and/or to be used with caution.

Based on the adverse events (AEs) observed in the dose escalation phase of the first-time-in-human (FTIH) study MEK111054, the maximum tolerated dose was established at 3.0 mg once daily (QD), and the recommended Phase II dose (RP2D) of trametinib was identified as 2.0 mg QD.

Pharmacodynamics

Pre- and post- (day 15) treatment tumor biopsies were performed for evaluation of pharmacodynamic (PD) markers in patients with metastatic melanoma in the first monotherapy trial of trametinib conducted (MEK111054). Doses remained stable for the 15 days of treatment and were 0.5, 1.0 or 2.0mg/day. PD markers evaluated included percent change from baseline of pERK, Ki67, and p27. Trough levels of trametinib were also obtained at day 15. PD responses in this study were dose-related, with minimal PD effects seen at 0.5mg/day, and robust changes reported at 2.0mg/day. The median change observed at a dose of 2 mg

daily was 62% inhibition of pERK, 83% inhibition of Ki67, and a 175% increase in p27, confirming inhibition of the MAPK/ERK pathway. Correlations were also reported between PD response and trough concentrations of trametinib on day 15. Monte Carlo simulations predict that 86% of subjects will exceed the target concentration of 10ng/mL at the 2mg/day dose.

Trametinib 2.0 mg once daily was administered in the Phase II and Phase III studies. After accounting for the effect of lactate dehydrogenase (LDH), a known prognostic marker in subjects with melanoma, subjects with exposure above the median value had longer progression-free survival (PFS) than those below the median exposure with hazard ratio (HR) <1. The relationship with exposure was more pronounced in the Phase II study compared to the Phase III study which may be related to the lower exposure observed in subjects enrolled in the Phase II study. The higher exposure in the Phase III study may suggest that the drug response is starting to plateau and data are less likely to show /an exposure-response.[4]

Safety and Efficacy

The most common adverse reactions in the trametinib arm (n=211) from the randomized, open-label study of trametinib versus chemotherapy in patients with BRAF^{V600E} or ^{V600K} mutation –positive melanoma included the following: rash (57%), dermatitis acneiform (19%), dry skin (11%), pruritus (10%), paronychia (10%), diarrhea (43%), stomatitis (15%), abdominal pain (13%), lymphedema (32%), hypertension (15%), and hemorrhage (13%).

See section 5.1 and the trametinib Investigator's Brochure for additional safety information on trametinib and section 1.5 for safety and efficacy data when trametinib is combined with dabrafenib in BRAF mutant melanoma.

1.4 Dabrafenib

Dabrafenib is a potent and selective inhibitor of BRAF kinase, and inhibits phosphorylation of MEK and ERK *in vitro*, inhibits cell proliferation, and achieved tumor regression in xenograft cancer models that encode BRAF^{V600E}. [5] Dabrafenib is approved as monotherapy for the treatment of patients with unresectable or metastatic melanoma with BRAF V600E mutations, and in combination with trametinib for the treatment of patients with unresectable or metastatic melanoma with BRAF V600E or V600K mutations

Dabrafenib is under development for the treatment of advanced cancer subjects with BRAF mutant tumors, which have been identified at a high frequency in specific cancers including approximately 40-60% of melanoma, 30 to 50% of papillary thyroid, 5 to 20% of colorectal cancer, and approximately 30% of ovarian cancer.

Please also review the latest version of the Investigator's Brochure for trametinib and dabrafenib for updated background information on each product and the number of clinical trials ongoing.

1.4.1 Effects in Humans

The effect of dabrafenib in subjects with a variety of cancers has been evaluated in a number of studies, and additional studies are ongoing. [5]

Pharmacokinetics

Two metabolites of dabrafenib were characterized and may contribute to the clinical activity of this drug. GSK2285403 (hydroxy-metabolite) pharmacokinetics paralleled that of parent while the desmethyl- (GSK2167542) metabolites exhibited a longer half-life and accumulated following repeat dosing. Similar to parent concentrations, exposure for all metabolites showed a less than dose proportional increase with repeat dosing.

Results following single dose administration showed a total recovery of radioactivity of 93.8 % of the dose with fecal excretion being the major route of elimination, accounting for 71.1% of the dose.

The current recommendation is to administer dabrafenib under fasting conditions, either one hour before or 2 hours after a meal. Preliminary results of the food effect study showed a decrease in dabrafenib C_{max} and AUC(0-∞) after single dose administration.

Preliminary results of the effect of repeat dose administration of dabrafenib 150 mg BID on the single dose pharmacokinetics of midazolam, a CYP3A4 probe, showed a decrease in midazolam exposure, indicating that dabrafenib induces CYP3A4-mediated metabolism (moderate to potent). It may also induce other enzymes such as CYP2B6, CYP2C8, CYP2C9, and CYP2C19, as well as UDP glucuronosyl transferase (UGT) and transporters. Co-administration of dabrafenib and drugs that are affected by the induction of these enzymes may result in decreased concentrations and loss of efficacy. In preliminary studies, dabrafenib was a substrate for human P-glycoprotein (Pgp) and murine breast cancer resistant protein 1 (Bcrp1) *in vitro*. However, these transporters have minimal impact on dabrafenib oral bioavailability and elimination, and the risk of a drug-drug interaction is minimal. [5]

In addition, CYP2C8, CYP3A4 and to a lesser extent CYP2C9 and CYP2C19 are involved in the oxidative metabolism of dabrafenib. *In vitro*, selective inhibitors of CYP 2C8 and CYP3A4 reduced the intrinsic clearance of dabrafenib. These results suggested that dabrafenib has the potential of being a victim of drug-drug interactions upon co-administration with strong CYP2C8 and CYP3A4 inhibitors and inducers.[5]

This protocol prohibits or caution against the use of medications with the potential for drug interactions with dabrafenib and/or trametinib. See section 4.5 (Concomitant Medications) and section 11.2 (Appendices) for the categories of medications that are prohibited and/or to be used with caution.

Pharmacodynamics

Based on results from the dose escalation part of Study BRF112680 (Part 1) in patients with V600 mutant-positive melanoma, 150mg BID is predicted to provide, on average, adequate inhibition of pERK (80%). [5]

Safety as Monotherapy

As summarized in the table below (from the dabrafenib 2014 IB)[5] the following adverse events were considered related to dabrafenib when administered as monotherapy across company-sponsored clinical trials (n=578). Approximately 30% of these patients received dabrafenib treatment for >6 months. Frequencies are as follows: very common (≥10%), common (≥1% and <10%), uncommon (≥0.01% and <1%), and rare (≥0.01% and <0.1%).

Frequency	Adverse Event
Very Common	Skin papilloma, papilloma
	Decreased appetite
	Headache
	Cough
	Nausea, vomiting, diarrhea
	Skin effects (rash, hyperkeratosis), alopecia, palmar-plantar erythrodysesthesia syndrome
	Arthralgia, myalgia, pain in extremity
	Asthenia, fatigue, pyrexia, chills
Common	Squamous cell carcinoma (SCC), including SCC of the skin, SCC in situ (Bowen’s disease), and keratoacanthoma Acrochordon (skin tags)
	Seborrheic keratosis
	Hypophosphataemia
	Constipation
	Skin effects (Actinic keratosis, Skin lesion, Dry skin, Erythema)
Influenza-like illness	
Uncommon	New primary malignant melanoma
	Hypersensitivity
	Uveitis
	Pancreatitis
	Renal failure, acute renal failure

See section 5.2.5 for additional safety information on dabrafenib and section 1.5 for safety and efficacy data when dabrafenib is combined with trametinib in BRAF mutant melanoma.

